- Any form of inflammatory arthritis (e.g. RA, gout, pseudogout, lupus, etc.)

Page 6 of 41

- Significant co-morbid conditions as determined by the investigator (e.g. malignancy, renal, hepatic disease, etc.)
- Known or suspected psychological disorder
- 3. List any restrictions on use of other drugs or treatments. N/A

Statistical Considerations

1. **Is stratification/randomization involved?** Yes.

► IF YES, describe the stratification/ randomization scheme.

Block randomization will be completed *a priori* via a random number generator. 20 subjects will be allocated to group within each block (10 per group). Group assignments will be sealed in an opaque envelope each containing a number from 001-090. Each subject will be randomly assigned in a 1:1 ratio to receive one of the treatments (group) described below. Randomization envelope #001 will be used for the first subject, #002 for the second and so on. Group assignment for enrolled subjects will be determined intra-operatively. Prior to the determination of group assignment, the treating surgeon will drill two tibial tunnel guide pins, assessing pin placement via fluoroscopy, to ensure that one tunnel is anterior and the other is posterior to the 35% line. The sealed envelope will then be opened following confirmation of guide pin placement, and the procedure will be performed in accordance with the randomized group assignment.

Patients with a prior history of ACL reconstruction who enter the study post-operatively will be assigned to the appropriate group based on graft placement (anterior or posterior) that was performed for clinical care.

► IF YES, who will generate the randomization scheme?

X Other: Study coordinator

2. What are the statistical considerations for the protocol?

We have designed the study in a way that will make it easy to match an appropriate statistical procedure to test our primary hypotheses. Subjective and objective measures of knee function will be evaluated at 6, 12 and 24 months post-surgery.

3. Provide a justification for the sample size used in this protocol.

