Sample size for IKDC and KT-1000 side-side differences are calculated based on the expected between-group differences observed at the final time point of this study – 24 months post reconstruction. In order to observe a 2.4 mm between group differences in joint laxity symmetry, we need 40 patients per group. This estimate accounts for up to 3.5 mm in variability in KT-1000 side-side measurement change from pre-post-surgery. Further, we need 55 patients per group to detect a 8-point difference in IKDC score between groups assuming variability of 12 points in IKDC score. These estimates account for 20% attrition. Estimates are calculated to find statistically significant differences allowing for 5% type I error rate and power exceeding 80%.

4. What is your plan for primary variable analysis?

We will use independent t tests to determine group differences at each time point.

Page 7 of 41

5. What is your plan for secondary variable analysis?

We do not plan to use a secondary variable analysis.

6. Have you been working with a statistician in designing this protocol? Yes **IF YES, what is their name?** [name]

Page 8 of 41

- 7. Will data from multiple sites be combined during analysis? Yes
 - 7(a). Does the study involve randomization? Yes

IF YES, will randomization be done at each site or among sites? Randomization will be done at each site.

- 7(b). Has the sample size calculation considered the variation among sites? Yes
- 7(c). When combining the data from multiple sites to assess the study results, is the effect of the treatment to be tested (or the association to be tested) assumed to be the same across sites or vary among sites? What is the modelling strategy?

Yes. The effect of the treatment (placement of tibial tunnel) will be assessed using standard measures of joint laxity and patient-reported function. We have no evidence to believe that these outcomes differ between sites under standard protocols.

7(d). Is there a common protocol used in all sites? NO

IF NO, how will differences among sites, such as those related to the implementation, inclusion criteria, patient characteristics, or other sites characteristics, be considered to assess the study results?

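### The sample-size justification asks for 110 patients for IKDC while the plan randomises 90 and targets 75 completers; nothing reconciles these figures, and 55 and 40 per group do not follow from one rule

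*Combined protocol and SAP*

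**What the plan says.** Statistical Considerations, item 3 gives two sizes, both for the 24-month comparison. For the 2.4 mm KT-1000 difference "in joint laxity symmetry, we need 40 patients per group", and "This estimate accounts for up to 3.5 mm in variability in KT-1000 side-side measurement change from pre-post-surgery". For IKDC, "we need 55 patients per group to detect a 8-point difference in IKDC score between groups assuming variability of 12 points in IKDC score". One statement then covers both: "These estimates account for 20% attrition", with the estimates "allowing for 5% type I error rate and power exceeding 80" per cent. Sidedness is not stated, nor whether the 5% applies to each of the two primary comparisons or is shared between them. Item 4 names independent t tests.

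The other counts are:

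- Human Participants, Subjects item 1: 75 prospective patients to complete, plus 45 retrospective.
- Subjects item 2: attrition of up to 20%.
- Subjects items 3 and 4: 90 prospective patients in total across the two sites. The 55 given in item 4 for the lead site is its share of the 90, not a group size.
- Statistical Considerations, item 1: 1:1 allocation, and "Group assignments will be sealed in an opaque envelope each containing a number from 001-090". Patients who enter after surgery are grouped by the placement they already received.

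On sites, item 7(b) reads "Has the sample size calculation considered the variation among sites? Yes", and 7(c) adds "We have no evidence to believe that these outcomes differ between sites under standard protocols".

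**The concern.** Item 3 exists to justify the sample size used, and for the first-listed primary comparison it justifies a different number from the one planned. If all 90 envelopes are used as intended, the randomised part ends 20 patients below the stated IKDC requirement. Anyone reading an inconclusive IKDC result could point to that gap, and the plan offers no answer. A reader also cannot check the power claim, because the rule behind 55 and 40 is not given and the two figures do not look like products of the same rule.

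**Working it through.** **Inputs.** From item 3: differences of 8 points and 2.4 mm; variability of 12 points and up to 3.5 mm, read here as standard deviations (an assumption); 20% attrition; 5% type I error; power above 80%. From item 1: 1:1 allocation. From item 4: two-sample t test. Power figures use the noncentral t distribution.

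**Step 1: the counts.**

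- Stated IKDC need: 2 × 55 = 110 enrolled; 110 × 0.8 = 88 evaluable.
- Provided: 90 randomised, about 45 per group; 90 × 0.8 = 72 evaluable, or the 75 targeted.
- Gap: 110 − 90 = 20, and 20/110 = 18%.
- 75 of 90 implies 1 − 75/90 = 16.7% loss, not 20%. The pair fits 75 × 1.2 = 90, but not 75/0.8 = 93.75.
- With the post-operative entrants: 90 + 45 = 135, which is not 110 either.

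**Step 2: can one rule give both 55 and 40?** The standardised effects are 8/12 = 0.667 and 2.4/3.5 = 0.686. Required size varies very nearly as 1/d², so under one rule the ratio of IKDC to KT-1000 size is (0.686/0.667)² = 1.058. The stated ratio is 55/40 = 1.375. A single site-variation multiplier applied to both would cancel and leave the ratio unchanged.

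Sizes per group at 80% power:

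| Rule | IKDC | KT-1000 |
|---|---|---|
| Stated in item 3 | 55 | 40 |
| Two-sided 5%, t, n/0.8 | 36.31/0.8 = 45.4 | 34.37/0.8 = 43.0 |
| Two-sided 5%, normal, n/0.8 | 35.32/0.8 = 44.2 | 33.38/0.8 = 41.7 |
| Two-sided 5%, normal, n × 1.2 | 42.4 | 40.06 |
| Two-sided 2.5%, t, n/0.8 | 44.05/0.8 = 55.07 | 41.71/0.8 = 52.1 |
| One-sided 5%, t, n/0.8 | 28.52/0.8 = 35.7 | 27.00/0.8 = 33.75 |

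Each stated figure can be matched alone: 40 by the fourth row, 55 by the fifth. No row gives both. A wider scan (one- and two-sided; alpha 5%, 2.5% and 1%; power 75% to 99%; t or normal; n/0.8, n × 1.2 or no inflation; no site term) also found none. Its closest rule gave 50 and 46 and so missed one figure by 6 patients.

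**Step 3: do the stated sizes meet the stated power?** After 20% loss, 55 becomes 44 and 40 becomes 32 per group.

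| Test | IKDC, 44 per group | KT-1000, 32 per group |
|---|---|---|
| Two-sided 5% | 87.1% | 77.0% |
| One-sided 5% | 92.7% | 85.7% |

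Two-sided, 32 per group reaches 80% only if the KT-1000 SD is about 3.37 mm or less.

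**Step 4: what the planned 90 deliver, two-sided t test.**

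| Completers | Alpha per endpoint | IKDC | KT-1000 |
|---|---|---|---|
| 72 (36 per group, 20% loss) | 5% | 79.7% | 81.8% |
| 72 (36 per group, 20% loss) | 2.5% | 70.4% | 73.1% |
| 75 (37 and 38) | 5% | 81.3% | 83.4% |
| 75 (37 and 38) | 2.5% | 72.4% | 75.1% |

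Blocks of 20 do not divide 90 evenly, but a 50:40 split with 20% loss changes the 5% figures only to 79.2% and 81.4%.

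**The case against.** The plan never claims that one rule produced both sizes, and power above 80% is a floor that 55 may exceed. The hypotheses are directional, which lends some support to a one-sided reading, and under it both sizes comply. The 3.5 mm is an upper limit, and it describes a pre-to-post change. Site variation is said to have been considered. Item 3 speaks of patients per group without saying randomised, and item 1 places post-operative entrants in the appropriate group, so counting them gives 135, more than 110.

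Part of this stands. The shortfall for KT-1000 depends on a two-sided test and on the SD ceiling. But item 3 gives a single statement of error rate, power and attrition for both sizes and shows no site term, while item 7(c) reports no evidence that outcomes differ between sites. No section says that the 45 count towards the 55 per group, and as they are not randomised they cannot support the size of a randomised comparison.

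Two stronger readings are tempting:

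- A reader might infer that the trial is 20 patients too small. The documents do not show this: at 5% per endpoint the 90 give about 80% and 82% power.
- A reader might infer the opposite, that 90 is adequate and only the wording of item 3 is wrong. The documents do not show that either. A 2.5% share for each of the two primary comparisons reproduces 55 for IKDC, and on that basis 90 patients give only about 70% and 73%. The plan states no such split, and the same rule gives about 52 for KT-1000, so this too remains a conjecture.

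**Conclusion.** The inconsistency is real and can be seen from the text alone: 110 needed, 90 provided, 75 to complete, with nothing linking them. That part needs no assumption beyond treating the 45 post-operative entrants as outside the randomised sample. The second part, that 55 and 40 do not share a rule (ratio 1.375 against 1.058), rests on reading variability as an SD and on there being no endpoint-specific site allowance. The third, that 40 per group misses the power floor at 77.0%, also rests on a two-sided 5% test and an SD of 3.5 mm. Which of 110 and 90 is the error cannot be settled from the documents. The point should be fixed because the published justification does not support the number the trial uses, and the power actually planned ranges from about 70% to above 80% according to choices that the plan leaves open.

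**What to change.** In Statistical Considerations, item 3:

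1. State the sidedness, whether 5% applies to each primary comparison or is shared between the two, the target power, the SDs (saying that they are SDs) and the attrition formula, for example n/(1 − 0.2).
2. Recompute both endpoints by that one rule in place of 55 and 40. If 55 has another basis, such as a shared alpha or a site allowance, give it.
3. Restate the power that the 90 planned patients deliver, and replace the claim of more than 80% with the figure that applies. For a two-sided t test at 20% loss this is 79.7% (IKDC) and 81.8% (KT-1000) at 5% per endpoint, or 70.4% and 73.1% at 2.5%. At 75 completers and 5% it is 81.3% and 83.4%.
4. Reconcile 110, 90 and 75 in item 3 and in the Subjects items, noting that 20% loss of 90 leaves 72.
5. State that the 45 non-randomised entrants do not count towards the randomised sample size.

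This changes wording only and adds no patients. The cost is a less favourable stated power: marginally below 80% for IKDC at 5% per endpoint, and clearly below it for both endpoints if the 5% is shared.

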This study is designed as a prospective, double arm, study. Patients with a diagnosed rupture of the anterior cruciate ligament (ACL) who are scheduled for surgical reconstruction will be considered for enrollment. Eligible subjects will be allocated to one of two groups based on the location of the tibial tunnel (anterior vs. posterior) during the surgical procedure. The study population will consist of patients 16-50 years of age, with ACL rupture, who are seeking surgical reconstruction. Patients with active infection, previous ACL surgery, multiple ligament knee injury, previous joint modifying surgery in target knee within 12 months of planned procedure, flexion contracture, valgus alignment, pathologic ligament instability, knee osteoarthritis, inflammatory joint disease, metabolic bone disease (marked bone loss or moderate to severe osteoporosis), comorbidities such as type 1 diabetes, connective tissue disorder, or morbid obesity (BMI ≥35) will be excluded.

Subjects will return for follow-up visits at 6, 12, and 24 months post-surgery. If a subject is unable to come to UVA for a follow up visit, a home visit can be arranged with a member of the study team. Note that all data cannot be collected through a home visit, but instead only the subjective outcomes and some aspects of the knee exam can be collected. Follow up will be completed at 24 months for all enrolled subjects. Additionally, subjects with a prior ACL reconstruction who meet all study criteria, may enter the study at any post-operative time point (retrospective aspect of the study).

The primary objective of this study is to collect data on subjective and objective measures of knee related function in subjects with an anterior vs. posterior placed tibial tunnel through 24 months postoperative follow-up.

The primary analysis will compare groups at 24-months post-op with regard to:

- 1. Clinically significant difference of at least 8 points on IKDC score
- 2. Clinically significant difference of at least 2.4 mm knee joint laxity (KT-1000)

Background

1. Provide the scientific background, rationale and relevance of this project.

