Although extensive research has been carried out on ACL Femoral Tunnel placement, very little attention has been given to the tibial tunnel. Staubli et al. suggest that the tibial tunnel be placed in the center of the ACL footprint, which they described as being approximately 43% of the way (anterior to posterior) across the proximal tibia at its widest extent. However, others have suggested that a more anterior placement may yield improved biomechanical and clinical results. The center of the ACL footprint and the posterior aspect of the anterior horn of the lateral meniscus does not yield tibial tunnel placement a consistent percentage of the way across the tibial plateau⁴, therefore, guidelines should be based on intraoperative fluoroscopic measurements. However, the question remaining is what percentage of the A-P distance across the tibia is the ideal location for the tibial tunnel in ACL reconstruction. This study will help answer that question.

Page 4 of 41

Hypothesis to be Tested

Objective:

Compare anterior versus posterior tibial tunnel placement for ACL reconstruction in a prospective randomized clinical trial.

Hypotheses:

A more anterior placed tibial tunnel will yield improved outcomes with regard to:

- 1. Improved knee-specific self-reported function (IKDC)
- 2. Decreased knee joint laxity (KT-1000)

Study Design: Biomedical

- 1. Will controls be used? No
- 2. What is the study design?

Single-blind, randomized controlled clinical trial

3. Does the study involve a placebo? No

Human Participants

Ages: 16-50

Sex: Male and Female

Race: All

Subjects- see below

INSTRUCTIONS: For question 1-4 below insert an exact #. Ranges or OPEN is not allowed. This # should be the maximum # you expect to need to enroll (i.e. sign consent) If you are only collecting specimens the number of participants should equate to the # of specimens you need. If you are collecting only data from a chart review the number should designate the number of subjects whose medical records you plan to review. Age/ Sex/Race criteria should designate the demographics of participants from whom you will obtain the specimen/data.

- **1.** Provide target # of subjects (at all sites) needed to complete protocol.75(prospective aspect) 45 for retrospectice (UVA only)
- 2. Describe expected rate of screen failure/ dropouts/withdrawals from all sites.

We expect up to a 20% rate of attrition due to loss of follow up.

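### The primary t test leaves out the baseline scores and site; a pre-specified ANCOVA in the randomised patients would be a near-free gain in precision

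*Combined protocol and SAP*

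**What the plan says.** The protocol summary sets the time point: "The primary analysis will compare groups at 24-months post-op with regard to" IKDC and KT-1000 laxity. Item 4 of Statistical Considerations gives the method: "We will use independent t tests to determine group differences at each time point". No covariate is named.

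Both outcomes are listed at the screening visit (Study Procedures, Visit 1), before surgery. Item 3 describes the 3.5 mm used for laxity as "variability in KT-1000 side-side measurement change from pre-post-surgery", so the KT-1000 test may be meant for change from baseline. Item 4 does not say.

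On site, item 7(a) answers: "Randomization will be done at each site". Item 7(b) says the sample size considered variation among sites. Item 7(c), asked for a modelling strategy, names none and replies: "We have no evidence to believe that these outcomes differ between sites under standard protocols". Item 7(d) then says there is no common protocol. Its explanation adds that screening is similar and the enrolment criteria are the same at each practice, and that unspecified statistical steps after data collection will account for differences in patient characteristics. That is the only adjustment mentioned, and it names no model or covariate.

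On post-operative entrants, item 1 says: "Patients with a prior history of ACL reconstruction who enter the study post-operatively will be assigned to the appropriate group based on graft placement".

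**The concern.** A 24-month comparison that ignores a pre-operative measurement of the same scale leaves explainable variation in the error term. If allocation is balanced within site and the sites differ, a test without site also treats between-site variation as noise.

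A second gap concerns pre-specification. The plan intends some adjustment but leaves its form open until the data are complete, and it does not say how that adjustment relates to the item 4 test. Naming the model now settles which estimate is primary. That benefit does not depend on how well baseline predicts outcome.

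At stake is a modest amount of power and a clear primary estimate. The validity of the randomised comparison is not in question.

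**Working it through.** **Inputs from the documents.** IKDC difference 8 and variability 12, read as the SD (item 3). Type I error 5%, taken as two-sided. 1:1 allocation in blocks of 20 (item 1). 90 prospective patients, 55 of them at the main site (Human Participants items 3 and 4), so 90 − 55 = 35 at the other. Attrition: "We expect up to a 20% rate of attrition due to loss of follow up" (item 2).

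**Assumed.** The correlation r between baseline and 24-month IKDC, varied from 0 to 0.5, and any site gap.

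**The plan's own figure.** At 80% power the t test needs 37 per group, or 47 after dividing by 0.8. At 85% it needs 42 (53), and at 90% it needs 49 (62). Item 3's 55 per group leaves 55 × 0.8 = 44 evaluable, with 87.1% power. That agrees with the stated power above 80%.

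**Power at the planned randomised enrolment.** 90 × 0.8 = 72, or 36 per arm. The noncentrality is 8 / (12 × √(2/36)) = 2.83 on 70 df, which gives 79.7%. With the 75 completers in Human Participants item 1 it is 81.3%.

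**Adding baseline.** The residual SD becomes 12 × √(1 − r²). At r = 0.3 this is 11.45, and the noncentrality is 8 / (11.45 × √(2/36)) = 2.96 on 68 df, which gives 83.2%. The formula ignores chance covariate imbalance, so the model with baseline and site was also simulated (100,000 runs per scenario, sites of 55 and 35, blocks of 20 within site, random loss to 72, no site gap):

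| r | t test, simulated | ANCOVA, formula | ANCOVA, simulated |
|---|---|---|---|
| 0 | 79.6% | – | 78.9% |
| 0.1 | 79.6% | 80.0% | 79.3% |
| 0.2 | 79.5% | 81.2% | 80.4% |
| 0.3 | 79.4% | 83.2% | 82.3% |
| 0.4 | 79.7% | 86.0% | 85.5% |
| 0.5 | 79.6% | 89.6% | 89.0% |

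The simulated 82.3% at r = 0.3 is what a t test reaches with 77 patients, and 77/72 = 1.07, or roughly 7% more patients. The shortcut 1/(1 − r²) = 1.10 overstates this. With 75 retained, simulated ANCOVA power is 80.3% at r = 0, 84.0% at 0.3 and 90.2% at 0.5. With 44 per group, the formula gives 90.0% at r = 0.3 against 87.1%.

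**Adding site (r = 0.3, 72 retained, SD 12 within site).**

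| Assumed site gap | t test | Baseline only | Baseline and site |
|---|---|---|---|
| None | 79.4% | 82.4% | 82.3% |
| 4 points | 78.7% | 81.8% | 82.5% |
| 8 points | 76.1% | 79.2% | 82.5% |

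Across the values of r tried, the site term costs 0.1 to 0.2 points when the sites do not differ. Under an 8-point gap it gains about 3 (82.5 − 79.2).

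The fall of the t test to 76.1% depends on how SD 12 is read. An 8-point gap adds variance 64 × (55 × 35)/90² = 15.2. If 12 is the within-site SD, the overall SD is √(144 + 15.2) = 12.6. If 12 already includes site variation, the overall SD stays at 12 and t-test power stays at about 80%.

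**Single allocation list.** Item 1's one run of envelopes, 001 to 090, could mean a single list. Under that reading, with an 8-point gap, power is 75.3% for the t test and 81.9% for ANCOVA with site, so the site term helps either way.

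**KT-1000.** Let Y be the 24-month value and X the baseline. Regressing Y − X on arm, X and site only lowers the coefficient of X by 1, so the arm estimate is identical to that from regressing Y. No KT-1000 gain is quoted, because 3.5 mm is described as variability of change and item 4 does not say which quantity is tested.

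**The case against.** The strongest reply is that an unadjusted test in a randomised trial is a legitimate choice and that the gain rests on a correlation the documents do not supply. Both points stand. Pre-operative IKDC in an injured knee may predict poorly, and at r of 0.1 or less the model gains nothing.

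A reader might infer more than the documents support:

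- *That the t test is biased or inflates type I error when site is left out.* It does neither. With per-site blocks its simulated type I error is 4.2% under an 8-point gap and 4.75% under a 4-point gap. With a single list it is 5.0%.
- *That the trial was planned at only 80% power.* Item 3's own figure gives 87.1%. The 79.7% follows from enrolling 90 and losing the full 20%. The mismatch between 90 and 2 × 55 = 110 is a separate matter.
- *That site differences will pull power down to 76%.* This needs an assumed gap as large as the target effect and an SD of 12 that excludes site variation. Item 7(b) points the other way.
- *That the sites run materially different trials.* Item 7(d) denies a common protocol, but it also reports shared enrolment criteria, and the Biomedical Research section prescribes the same rehabilitation for all.
- *That the 45 post-operative entrants are in the primary test.* The plan does not say so.

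**Conclusion.** The point holds as an improvement in precision and pre-specification, not as an error. With 72 evaluable patients, ANCOVA on baseline and site changes IKDC power by about −0.7 points at r = 0, +3 at r = 0.3 and +9 at r = 0.5. At item 3's sample size the gain at r = 0.3 is also about 3 points (87.1% to 90.0%). The site term is close to free if the sites are alike and is worth about 3 points under an assumed 8-point gap.

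These sizes rest on SD 12, a difference of 8, a two-sided 5% test and the assumed r. For KT-1000, the claim that baseline is unused holds only if the 24-month value, rather than the change, is what item 4 tests. The case for naming the model in advance rests on none of these figures.

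**What to change.** In item 4, replace the t test at each time point with a linear model, fitted in the randomised prospective patients, of the outcome on arm, baseline value of the same measure and site. State that the 24-month arm effect is primary. The same model serves KT-1000 whether it is expressed as value or change.

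Keep the intention in item 7(d) to account for patient characteristics, but make it a sensitivity analysis with covariates named before the data are seen.

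The post-operative entrants are not randomised and have no study-collected pre-operative baseline, so they cannot enter this model. Whether they belong in the primary comparison should be decided and stated separately. If they were meant to be included, that decision changes the analysis population and is not free.

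The rest costs wording only, with no new visits, data or change to allocation. The statistical price is at most about 0.7 points of power if baseline proves uninformative. The plan would also need a line on how a missing Visit 1 value is handled.
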